5.9.2 STATISTICAL ANALYSIS

Data will be entered into SPSS statistical software. Normally distributed continuous data will be analysed with Student's t test. Chi square test will be used for categorical or nominal data and Mann-Whitney U test will be used on non-normally distributed continuous or ordinal data. P < 0.05 is taken as level of significance.

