5.7 Study Design

This is a randomised control trial. Nulliparas, who are at 34 – 36 weeks who attend Antenatal clinic in UMMC and reported night sleep duration of 5 hours or less on average in the last 1 month will be informed regarding this study. Patient information sheet will be provided for those who fulfilled initial eligible criteria. Those who agreed to participate will be asked to provide written consent, and agree to participate in this study, will be recruited.

They will be provided with Actisleep and taught on methods to use it. They need to wear it when they sleep at night 7 consecutive nights. Time in bed (TIB) and Time out of bed (TOB) need to be recorded every night.

After 7 days, they need return to Antenatal clinic, their sleep data will be retrieved from the Actisleep device. They can proceed with the study only if 3 days of usable readings are recorded. Randomisation with the intention to treat with a specific intervention or placebosham method will follow.

They will be randomised into 2 groups. interventional group or Placebo using sham method, based on a randomisation sequence generated using random.org in a random block of 4 or 8 sequence, generated by investigator not involved in the recruitment process. Randomisation is by the opening of sealed opaque and numbered envelope with lowest available envelope assigned in strict order.

A. Interventional Group: Eye masks and ear plugs.

Subjects are provided with eye masks and ear plugs to wear when they go to bed at night, for 7 consecutive nights. Time in bed(TIB) and time out of bed (TOB) needs to be recorded every night. They may remove the eye masks and ear plugs temporarily if they wake up from sleep at night.

At the end of 7 days, subjects will return to Antenatal clinic and have the Actisleep analysed and returned to the investigator.

Placebo Group

Subjects are provided with an elasticated headband to wear when they go to bed at night, for 7 consecutive nights. Headband shall be placed on their forehead loosely. Time in bed(TIB) and time out of bed (TOB) needs to be recorded every night.

[figure not shown]
At the end of 7 days, subjects will return to Antenatal clinic and have the Actisleep analysed and returned to the investigator.

Patients labor and neonatal outcomes will be analysed after they delivered.

At the end of the study, subject's satisfaction on their sleep quality will be assessed based on likert satisfaction scale.

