5.9 Statistical Analysis Plan

5.9.1 Sample size calculation

Our primary outcome is the increase of night sleep duration among nulliparas who reported short sleep duration of 5 hours or less.

There were no previous similar study regarding the use of Eye masks and Ear plugs in improving sleep in pregnancy.

Studies on ICU patients which increase of Total Sleep Time of 41 - 59% [10-12]. We postulate modest improvement of night sleep duration of 1 hour, which is 20% of 5 hours.

Assuming a normal distribution, standard deviation of 1.1hour, obtained from Lee and Gay[3]. 20 patients will be required in each arm to achieve statistical power of 90% (β 0.1) with alpha (α) of 0.05, 1 to 1 ratio across trial arms.

Factoring in dropout rate of 20%, we plan recruit 50 subjects for a suitably powered study

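### The primary 'increase' in sleep is undefined and the planned tests are unadjusted; regression on the run-in actigraphy baseline would settle the outcome and usually add power

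*Protocol*

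**What the plan says.** Protocol section 5.9.2 gives one rule for all continuous outcomes: "Normally distributed continuous data will be analysed with Student's t test", and "Mann-Whitney U test will be used on non-normally distributed continuous or ordinal data". It mentions no covariate.

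Section 5.9.1 gives the primary outcome: "Our primary outcome is the increase of night sleep duration among nulliparas who reported short sleep duration of 5 hours or less". The planning values are "We postulate modest improvement of night sleep duration of 1 hour, which is 20% of 5 hours" and "Assuming a normal distribution, standard deviation of 1.1hour", leading to "20 patients will be required in each arm to achieve statistical power of 90% (β 0.1) with alpha (α) of 0.05, 1 to 1 ratio". The text does not say whether the SD belongs to a single measurement or to a change, or whether the test is one- or two-sided.

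Section 5.7 sets a run-in before randomisation, in which women wear the actigraph: "They need to wear it when they sleep at night 7 consecutive nights". A woman goes on to randomisation only with 3 days of usable readings. A second 7-night recording follows under the allocated sleep aid.

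**The concern.** Each randomised woman contributes an objective, pre-randomisation measurement of the primary variable on the same device. The analysis text does not say how that measurement enters the primary comparison. Two readings are open:

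- **Week-2 values compared between arms.** The baseline is not used, and chance baseline differences stay in the error.
- **Change from week 1 compared between arms.** The baseline is used, but with a fixed weight of one, which is inefficient unless the two weeks are highly correlated.

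With t test or Mann-Whitney decided by the distribution, four primary analyses fit the text. At stake in a trial of about 20 per arm are the precision of the main result and whether one estimate in hours is fixed in advance, given that the trial is planned on a difference in hours.

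**Working it through.** **Inputs.** From section 5.9.1: difference 1 h, SD 1.1 h, alpha 0.05, 20 per arm, 50 recruited, 20% dropout. Assumptions, because the protocol is silent: a two-sided test; the week-1/week-2 correlation r, shown at 0.3, 0.5 and 0.7; equal SD in both weeks; both readings of the 1.1 h.

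**The protocol's own figure.** n per arm = 2(1.960 + 1.282)² × 1.1² / 1² = 25.4, so 26 (27 with the t distribution), against 20 stated. One-sided 0.05 at 90% gives 21 (22 with t); two-sided at 80% gives 19 (21 with t). The dropout step reproduces: 40 / 0.8 = 50.

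**Week-2 t test, 1.1 h as a single-occasion SD.** Noncentrality = 1 / (1.1 × √(2/20)) = 1 / 0.348 = 2.875 with 38 df. Power is 0.80 whatever r is (0.82 by the normal approximation).

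**Change-score t test, same SD.** SD of change = 1.1 × √(2(1 − r)).

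**ANCOVA, same SD.** Residual SD = 1.1 × √(1 − r²), with 37 df. Adjusting for a baseline that differs by chance between arms also inflates the variance, on average by 1 + 1/(2n − 4) = 1 + 1/36, about 3% at n = 20. The last column allows for this by averaging power over simulated normal baselines.

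| r | SD of change (h) | Change-score power | ANCOVA residual SD (h) | ANCOVA power, df loss only | ANCOVA power, with imbalance |
|---|---|---|---|---|---|
| 0.3 | 1.302 | 0.658 | 1.049 | 0.835 | 0.825 |
| 0.5 | 1.100 | 0.800 | 0.953 | 0.898 | 0.890 |
| 0.7 | 0.852 | 0.951 | 0.786 | 0.975 | 0.972 |

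At r = 0 to 0.1, ANCOVA has 0.789 to 0.793 against 0.800 for the week-2 t test. That is the worst case, a loss of about 1 point.

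**If 1.1 h is instead the SD of change.** The change-score t test has power 0.80 at every r. The ANCOVA residual SD is 1.1 × √((1 + r)/2), that is 0.887, 0.953 and 1.014 h. Power is 0.935, 0.898 and 0.859 at r = 0.3, 0.5 and 0.7, and 0.839 at r = 0.8, before a loss of up to about 1 point for imbalance. Here the gain over the change score shrinks as r rises.

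**Chance imbalance.** With a single-occasion SD of 1.1 h, the standard error of the between-arm baseline difference is 1.1 × √(2/20) = 0.35 h, about a third of the 1 h target.

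**The case against.** The strongest reply is that an unadjusted t test is valid under randomisation. Chance imbalance is already reflected in its standard error and is not bias, and covariate adjustment is often left to a separate analysis plan. The first part stands: this is not an error of validity. The second carries less weight, because section 5.9 is itself headed as the statistical analysis plan and names the tests.

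Several stronger readings are tempting but unsupported:

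- **That adjustment would recover most of the missing power.** This depends on r, which the protocol does not give, and on which SD 1.1 h is. Against the week-2 t test, r = 0.3 closes only about a quarter of the gap from 0.80 to 0.90 (0.025 / 0.10). At r = 0.7 with a single-occasion SD, the change score already has 0.95, so nothing is missing. The gap itself presumes a two-sided test; one-sided, 20 per arm give 0.88 to 0.89. The sample-size arithmetic is a separate matter.
- **That the baseline is wasted.** This is true only if week-2 values alone are compared.
- **That every woman has a 7-night baseline.** Seven nights are worn, but only 3 usable days are required.
- **That ANCOVA is never worse.** It loses about 1 point when r is near 0.
- **That choosing between t test and Mann-Whitney from the data seriously inflates false positives.** Simulated type I error with a Shapiro-Wilk pre-test in each arm (itself an assumption) was 5.3 to 5.5%. Nor does the protocol prevent a difference in hours from being reported.

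**Conclusion.** The point holds as a nearly free improvement and a definition that is needed, not as an invalid analysis. The firmest part rests on no assumption: the protocol does not define the increase, and the tests it names include no baseline term although every randomised woman has a baseline.

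The gain in power is conditional. With a single-occasion SD of 1.1 h and r = 0.5, ANCOVA raises power from 0.80 under either t test to about 0.89. At r = 0.3 it adds about 2 to 3 points over the week-2 test but about 17 over the change score. At r = 0.7 it adds about 17 over the week-2 test but only about 2 over the change score. If 1.1 h is the SD of change, the gain over the change score is large at low r and modest at high r. So the protocol does not allow one figure for the gain, but ANCOVA avoids the worst result of either t test, and it loses precision only when r is near 0.

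**What to change.** State the primary analysis in section 5.9.2 along these lines: mean actigraphic total sleep time per woman over usable week-2 nights, compared between arms by linear regression with week-1 mean total sleep time as covariate, women analysed in their allocated arm, result given as the adjusted difference in hours with a 95% CI. Say that this analysis is used whatever the normality check shows, with Mann-Whitney as a sensitivity analysis. Use the same model for WASO and sleep efficiency, and align the outcome wording in section 5.9.1.

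The same sentence should say how many usable nights week 2 needs (section 5.7 sets a minimum only for the run-in) and how women without usable week-2 data are handled, given the planned 20% dropout and the intention-to-treat wording.

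Cost: a few lines of text. No new visits, data or software are needed, since SPSS fits the model. The statistical price is one degree of freedom and up to about 1 point of power if r is near 0.

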5.10 Ethics of the study

This study is submitted to the UMMC Medical Research and Ethics committee, the local institutional review board for approval. Patient will be given an information sheet, have their oral queries addressed and written informed consent obtained to participate in the study.

GANNT Chart

Duration	July- August 2017	Aug – Sept 2017	Oct-Nov 2017	Dec- May 2018	June 2018	July 2018
Literature Review	✓					
Proposal preparation and Presentation	✓	✓				
Ethics Review			✓	✓		
Data Collection				✓	✓	
Data analysis and writing					✓	√
Thesis Submission						✓

- 15. The role of actigraphy in the study of sleep and circadian rhythms. Ancoli-Israel S, Cole R, Alessi C, Chambers M, Moorcroft W, Pollak CP Sleep. 2003 May 1; 26(3):342-92.
- 16. Validation of Watch-PAT-200 against polysomnography during pregnancy. O'Brien LM, Bullough AS, Shelgikar AV, Chames MC, Armitage R, Chervin RD J Clin Sleep Med. 2012 Jun 15; 8(3):287-94.

Data Collection form:

Interventional / Placebo

Subject no:		Actis	leep No:
Age:			
Height:	weight	::	
Gravida:	Para:	Abortion:	
Gestational Age:			
Address:			
Type of House: But	ngalow / Se	emi D / Terrace / Condomin	ium or Flat / Wooden /
Shared Bedroom (other than	partner) : Yes / No	
Bedroom: Air-cond	litioned / F	an / nothing	Night light : Yes / No
Bed : Single / Doub	le /		
Occupation:		shift work: Yes / No	Hours of work per day
Marital status : Sin	gle / Marri	ied / Widow	
Conception : Plann	ed / Unpla	anned	
Antenatal Problem	ns:		
1.			
2.			
3.			
Labor outcomes:			
Induction: Yes / N	0	Method : Fo	ley's / Prostaglandin
Amniotomy : Yes /	No		
Analgesics: Nil / E	ntonox / O _l	poids / Epidural / Combined	I
Mode of delivery:	SVD / Instr	umental / Caesarean Delive	ery
Estimated Blood lo	oss:		
Neonatal outcome	::		
Apgar score	1 minute	e 5 minute	
Birthweight :			

Cord pl	H: Bas	se Excess :	
Actisle	ер		
Model	Number		
Week 1	[
Day	Time in Bed	Time out of Bed	Self reported sleep(Hours)
1			
2			
3			
4			
5			
6			
7			
		l	
Week 2	2		
Day	Time in Bed	Time out of Bed	Self reported Sleep(hours)
1			
2			
3			
4			
5			

Indication:

NICU Admission: Yes / No

6

7

Satisfaction:

1. Since using the sleep aid for the last one week, I have slept better.

Strongly agree / agree / don't know / disagree / strongly disagree

2. Please rate your satisfaction with the use of your allocated sleep aid.

1 2 3 4 5 6 7 8 9 10

1: completely dissatisfied

10: completely satisfied
